10.3.2. Definition of SAE

If an event is not an AE per definition above, then it cannot be an SAE even if serious conditions are met (eg, hospitalization for signs/symptoms of the disease under study, death due to progression of disease).

An SAE is defined as any untoward medical occurrence that, at any dose:
1. Results in death
2. Is life-threatening
The term "life-threatening" in the definition of "serious" refers to an event in which the participant was at risk of
death at the time of the event. It does not refer to an event, which hypothetically might have caused death, if it
was more severe.
3. Requires inpatient hospitalization or prolongation of existing hospitalization
In general, hospitalization signifies that the participant has been detained (usually involving at least an overnight
stay) at the hospital or emergency ward for observation and/or treatment that would not have been appropriate in
the physician's office or outpatient setting. Complications that occur during hospitalization are AEs. If a
complication prolongs hospitalization or fulfills any other serious criteria, the event is serious. When in doubt as
to whether "hospitalization" occurred or was necessary, the AE should be considered serious.
Hospitalization for elective treatment of a pre-existing condition that did not worsen from baseline is not
considered an AE.
4. Results in persistent disability/incapacity
• The term disability means a substantial disruption of a person's ability to conduct normal life functions.
This definition is not intended to include experiences of relatively minor medical significance such as
uncomplicated headache, nausea, vomiting, diarrhea, influenza, and accidental trauma (eg, sprained ankle)
which may interfere with or prevent everyday life functions but do not constitute a substantial disruption.
5. Is a congenital anomaly/birth defect
6. Other situations:
• Medical or scientific judgment should be exercised in deciding whether SAE reporting is appropriate in
other situations such as important medical events that may not be immediately life-threatening or result in
death or hospitalization but may jeopardize the participant or may require medical or surgical intervention to
prevent one of the other outcomes listed in the above definition. These events should usually be considered
serious.
• Examples of such events include invasive or malignant cancers, intensive treatment in an emergency room
or at home for allergic bronchospasm, blood dyscrasias or convulsions that do not result in hospitalization,
or development of drug dependency or drug abuse.

10.3.3. Suspected Unexpected Serious Adverse Reactions Definition

A suspected unexpected serious adverse reaction (SUSAR) is defined as:

An event that is assessed as serious by the Investigator and/or Alexion that is not listed in the appropriate Reference Safety Information (IB) and has been assessed that there is at least a reasonable possibility that the event is related to the Investigational Medicinal Product by the Investigator and/or Alexion. Alexion has procedures that will be followed for the recording, medical assessment, and expedited reporting of SUSARs that are consistent with global regulations, legislation, and guidance documents.

Suspected unexpected serious adverse reactions will undergo expedited reporting to the national regulatory authorities, IRBs/IECs, and Investigators following local regulatory reporting requirements where applicable.

10.3.4. Recording and Follow-Up of AE and/or SAE

Recording of AE and/or SAE

• When an AE/SAE occurs, it is the responsibility of the Investigator to review all documentation (eg, hospital progress notes, laboratory reports, and diagnostics reports) related to the event.

Recording of AE and/or SAE

- The Investigator will then record all relevant AE/SAE information in the eCRF.
- It is not acceptable for the Investigator to send photocopies of the participant's medical records to Alexion or designee in lieu of completion of the AE/SAE eCRF page.
- There may be instances when copies of medical records for certain cases are requested by Alexion or designee. In this case, all participant identifiers, with the exception of the participant number, will be redacted on the copies of the medical records before submission to Alexion or designee.
- The Investigator will attempt to establish a diagnosis of the event based on signs, symptoms, and/or other clinical information. Whenever possible, the diagnosis (not the individual signs/symptoms) will be documented as the AE/SAE.

Assessment of Intensity

The Investigator will make an assessment of intensity for each AE and SAE reported during the study and assign it to one of the following categories from National Cancer Institute CTCAE v5.0, published 27 Nov 2017:

- Grade 1: Mild (awareness of sign or symptom, but easily tolerated)
- Grade 2: Moderate (discomfort sufficient to cause interference with normal activities)
- Grade 3: Severe (incapacitating, with inability to perform normal activities)
- Grade 4: Life-threatening
- Grade 5: Fatal

Changes in the severity of an AE should be documented to allow an assessment of the AE duration at each level of intensity to be evaluated. Adverse events characterized as intermittent require documentation of onset and duration of each episode, if the severity of the intermittent event changes.

An event is defined as "serious" when it meets at least 1 of the predefined criteria as described in the definition of SAE, NOT when it is rated as severe.

Assessment of Causality

- The Investigator is obligated to assess the relationship between the study intervention and each occurrence of each AE or SAE. An Investigator causality assessment must be provided for all AEs (both nonserious and serious). This assessment must be recorded in the eCRF and on any additional forms, as appropriate. The definitions for the causality assessments are as follows:
 - Not related: There is no reasonable possibility the study intervention caused the AE.
 - The AE has a more likely alternative etiology; it may be due to underlying or concurrent illness, complications, concurrent treatments, or effects of another concurrent drug.
 - The event does not follow a reasonable temporal relationship to administration of the study intervention.
 - Related: There is a reasonable possibility the study intervention caused the AE.
 - The AE has a temporal relationship to the administration of the study intervention.
 - The event does not have a likely alternative etiology.
 - The event corresponds with the known pharmaceutical profile of the study intervention.
 - There is improvement on discontinuation and/or reappearance on rechallenge.
- The Investigator will use clinical judgment to determine the relationship.
- Alternative causes, such as underlying disease(s), concomitant therapy, and other risk factors, as well as the temporal relationship of the event to study intervention administration will be considered and investigated.
- The Investigator will also consult the IB and/or Product Information, for marketed products, in his/her assessment.

Assessment of Causality

- For each AE/SAE, the Investigator **must** document in the medical notes that he/she has reviewed the AE/SAE and has provided an assessment of causality.
- There may be situations in which an SAE has occurred, and the Investigator has minimal information to include in the initial report to Alexion or designee. However, it is very important that the Investigator always make an assessment of causality for every event before the initial transmission of the SAE data to Alexion or designee.
- The Investigator may change his/her opinion of causality in light of follow-up information and send an SAE follow-up report with the updated causality assessment.
- The causality assessment is one of the criteria used when determining regulatory reporting requirements.

Follow-up of AEs and SAEs

- The Investigator is obligated to perform or arrange for the conduct of supplemental measurements and/or evaluations as medically indicated or as requested by Alexion or designee to elucidate the nature and/or causality of the AE or SAE as fully as possible. This may include additional laboratory tests or investigations, histopathological examinations, or consultation with other health care professionals.
- If a participant dies during participation in the study or during a recognized follow-up period, the Investigator will provide Alexion or designee with a copy of any postmortem findings including histopathology.
- New or updated information will be recorded in the originally completed eCRF.
- The Investigator will submit any updated SAE data to Alexion or designee within 24 hours of receipt of the information.

10.3.5. Reporting of SAEs

SAE Reporting to Alexion via Paper Safety Reporting Form

- 1. All SAEs will be recorded and reported to Alexion immediately and within 24 hours of awareness.
- 2. All SAEs will be reported using the Safety Reporting Form and submitted to Alexion Global Drug Safety (GDS). The Investigator must complete, sign, and date the SAE pages, verify the accuracy of the information recorded on the SAE pages with the corresponding source documents, and send a copy via email or facsimile to the contact information provided below:
 - Email: [contact] or Fax: [name]
- 3. Additional follow-up information, if required or available, should be entered into the eCRF and sent to Alexion GDS within 24 hours of the Investigator or study site staff becoming aware of this additional information via the reporting process outlined above.
- 4. For all SAEs, the Investigator must provide the following:
 - Appropriate and requested follow-up information in the time frame detailed above
 - Causality of the SAE(s)
 - Treatment of/intervention for the SAE(s)
 - Outcome of the SAE(s)
 - Medical records and laboratory/diagnostic information
- 5. All paper forms and follow-up information submitted to Alexion GDS **must** be accompanied by a cover page signed by the Investigator.
- 6. Paper source documents and/or reports should be kept in the appropriate section of the study file.

10.4. Contraceptive Guidance and Collection of Pregnancy Information

10.4.1. Definitions

Woman of Childbearing Potential (WOCBP)

A woman is considered fertile following menarche and until becoming postmenopausal unless permanently sterile (see below).

If fertility is unclear (eg, amenorrhea in adolescents or athletes) and a menstrual cycle cannot be confirmed before first dose of study intervention, additional evaluation should be considered.

Women in the Following Categories Are Not Considered WOCBP

- 1. Premenarchal
- 2. Premenopausal female with one of the following:
 - Documented hysterectomy
 - Documented bilateral tubal ligation or bilateral salpingectomy
 - Documented bilateral oophorectomy

For individuals with permanent infertility due to an alternate medical cause other than the above, (eg, Mullerian agenesis, androgen insensitivity), Investigator discretion should be applied to determining study entry.

Note: Documentation can come from the site personnel's review of the participant's medical records, medical examination, or medical history interview.

- 3. Postmenopausal female
 - A postmenopausal state is defined as no menses for 12 months without an alternative medical cause prior to the Day 1 Visit.
 - A high follicle-stimulating hormone (FSH) level in the postmenopausal range may be used to confirm a postmenopausal state in women not using hormonal contraception or hormonal replacement therapy (HRT). However, in the absence of 12 months of amenorrhea, confirmation with more than one FSH measurement may be required. In the absence of 12 months of amenorrhea the reason for not obtaining FSH levels should be documented by the Investigator at the time of Screening.
 - Females on HRT and whose menopausal status is in doubt will be required to use one of the non-estrogen hormonal highly effective contraception methods if they wish to continue their HRT during the study. Otherwise, they must discontinue HRT to allow confirmation of postmenopausal status before study enrollment.
- 4. Permanent sterilization at least 6 weeks prior to the Day 1 Visit.

10.4.2. Contraception Guidance

Contraceptive use by male or female participants should be consistent with local regulations regarding the methods of contraception utilized for those participating in clinical studies. If

$P_{a} \approx 74 \text{ of } 07$	
Page 74 of 97	
Alexion Confidential	
Alexion Confidential	

teratogenic effects are suspected to be transferred to a fetus/embryo from a female spouse/partner of a male participant, pregnancy follow-up information will be obtained for the partner who becomes pregnant (refer to Section 10.4.3.1). In these cases, follow-up will be conducted on the pregnant partner in the same manner as a female participant who becomes pregnant during the study.

10.4.2.1. Guidance for Female Participants

Female participants of childbearing potential must have a negative pregnancy test (serum) at Screening. Additional requirements for pregnancy testing during and after dosing with ALXN1850 are indicated in the SoA (Section 1.3).

The Investigator is responsible for the review of medical history, menstrual history, and recent sexual activity to decrease the risk for inclusion of a woman with an early undetected pregnancy.

The Investigator should evaluate the potential for contraceptive method in relationship to the first dose of ALXN1850.

Female participants of childbearing potential must use a highly effective method of contraception, including at least 1 of the following until at least 3 months after the final dose of ALXN1850.

- 1. Intrauterine device in place for at least 6 weeks prior to first dose of ALXN1850.
- 2. Progestogen-only hormonal contraception associated with inhibition of ovulation (either oral, injectable, or implantable) for at least 6 weeks prior to first dose of ALXN1850.
- 3. Intrauterine progestogen releasing system for at least 6 weeks prior to first dose of ALXN1850.
- 4. Bilateral tubal occlusion for at least 6 weeks prior to first dose of ALXN1850.
- 5. Combined (estrogen- and progestogen-containing) hormonal contraception (either oral, intravaginal, or transdermal) for at least 6 weeks prior to first dose of ALXN1850.
- 6. Surgical sterilization of the male partner (medical assessment of azoospermia is required if vasectomy was performed within 6 months prior to first dose of ALXN1850). Male partner is still required to use condom during sexual intercourse.
- 7. Sexual abstinence for female participants:
 - a. Sexual abstinence is considered a highly effective method only if defined as refraining from heterosexual intercourse. In this study, abstinence is only acceptable if consistent with the participant's preferred and usual lifestyle. Abstinent female participants must refrain from heterosexual intercourse for at least 3 months after the final dose of ALXN1850.

The following methods of contraception are considered unacceptable in this study:

- Periodic abstinence (calendar, symptothermal or post ovulation methods
- Withdrawal (coitus interruptus)
- Spermicides only
- Lactational amenorrhea method

- Female condom and male condom should not be used together

10.4.2.2. Guidance for Male Participants

Contraception is the responsibility of the heterosexually active male participants in the study, regardless of his female partner's method of contraception.

Male participants who have had a vasectomy > 6 months prior to the first dose of ALXN1850 must use a condom during heterosexual intercourse. Male participants who have had a vasectomy < 6 months prior to the first dose of ALXN1850 and those who have not had a vasectomy must use a condom with spermicide during heterosexual intercourse for at least 3 months after their final dose of ALXN1850.

10.4.2.2.1. Sexual Abstinence for Male Participants

Sexual abstinence is considered a highly effective method only if defined as refraining from heterosexual intercourse. In this study, abstinence is only acceptable if consistent with the participant's preferred and usual lifestyle. Abstinent male participants who become heterosexually active must use a condom with spermicide during intercourse.

Periodic abstinence (eg, calendar, symptothermal, or post ovulation methods for a female partner) is not considered a highly effective method of contraception for male participants.

Male participants must not donate sperm from the Day 1 Visit until at least 3 months after their final dose of ALXN1850.

10.4.3. Collection of Pregnancy Information

Pregnancy data will be collected during this study for all female participants and female spouses/partners of male participants from the first dose of ALXN1850 until 3 months after the final dose of ALXN1850 is administered. Any female participant who becomes pregnant during the study should be considered for discontinuation from the study intervention. Exposure during pregnancy (also referred to as exposure in utero) can be the result of either maternal exposure or transmission of study intervention via semen following paternal exposure. If a female participant or a male participant's female spouse/partner becomes pregnant during the conduct of this study, the Investigator must submit the "Pregnancy/Breastfeeding Reporting and Outcome Form" to Alexion GDS via facsimile or email. When the outcome of the pregnancy becomes known, the form should be updated and submitted to Alexion GDS. If additional follow-up is required, the Investigator will be requested to provide the information.

Exposure of an infant to study intervention during breastfeeding must also be reported (via the "Pregnancy/Breastfeeding Reporting and Outcome Form") and any AEs experienced by the infant must be reported to Alexion GDS via email or facsimile.

Pregnancy is not regarded as an AE unless there is a suspicion that the study intervention may have interfered with the effectiveness of a contraceptive medication. However, complications of pregnancy and abnormal outcomes of pregnancy are AEs and may meet the criteria for an SAE (eg, ectopic pregnancy, spontaneous abortion, intrauterine fetal demise, neonatal death, or congenital anomaly). Elective abortions without complications should not be reported as AEs.

Page 76 of 97
Alexion Confidential

10.4.3.1. Male Participants with Partners Who Become Pregnant

- The Investigator will attempt to collect pregnancy information on any male participant's female partner who becomes pregnant while the male participant is in this study. This applies only to male participants who receive ALXN1850.
- After obtaining the necessary signed informed consent from the pregnant female partner directly, the Investigator will record pregnancy information on the appropriate "Pregnancy/Breastfeeding Reporting and Outcome Form" and submit it to Alexion within 24 hours of learning of the partner's pregnancy. The female partner will also be followed to determine the outcome of the pregnancy. Information on the status of the mother and child will be forwarded to Alexion. Generally, the follow-up will be no longer than 3 months following the delivery date. Any termination of the pregnancy will be reported regardless of fetal status (presence or absence of anomalies) or indication for the procedure.

10.4.3.2. Female Participants Who Become Pregnant

- The Investigator will collect pregnancy information on any female participant who becomes pregnant while participating in this study. The initial Information will be recorded on the appropriate form and submitted to Alexion within 24 hours of learning of a participant's pregnancy.
- For all Alexion products, both in development or post approval, exposure during pregnancy must be recorded and the pregnancy followed, until the outcome of the pregnancy is known (ie, spontaneous miscarriage, elective termination, normal birth, or congenital abnormality), even if the participant discontinues the study intervention or withdraws from the study. The Investigator will collect follow-up information on the participant and the neonate and the information will be forwarded to Alexion. Generally, follow-up will not be required for longer than 3 months beyond the estimated delivery date. Any termination of pregnancy will be reported, regardless of fetal status (presence or absence of anomalies) or indication for the procedure.
- Pregnancy is not considered as an AE unless there is a suspicion that the study intervention may have interfered with the effectiveness of a contraceptive medication. While pregnancy itself is not considered to be an AE or SAE, any pregnancy complication or elective termination of a pregnancy for medical reasons will be reported as an AE or SAE. A spontaneous abortion (occurring at < 22 weeks gestational age) or still birth (occurring at > 22 weeks gestational age) is always considered to be an SAE and will be reported as such. Any poststudy pregnancy related SAE considered reasonably related to the study intervention by the Investigator will be reported to Alexion. While the Investigator is not obligated to actively seek this information in former study participants, he or she may learn of an SAE through spontaneous reporting.
- Any female participant who becomes pregnant while participating in the study will discontinue study intervention but will not be withdrawn from the study.

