^f A negative drug screen is required for participant enrollment. Results from drug screens collected at timepoints prior to dosing (Days -1, 7, 14, 21) are not required to confirm a negative result prior to dosing. The drug screen results received after sampling will be noted, and if positive, the participant will be discontinued from the study. If negative, the results will serve as clearance to proceed with dosing for future pre-dosing days. A positive drug test result a non-prescribed substance received at any visit will lead to discontinuation.

^g Pregnancy test must be performed on all participants of child-bearing potential at the specified time points. Additional pregnancy tests may also be performed at any time at the Investigator's discretion.

- ^h Predose and postdose abbreviated PEs are allowed at the predose or dosing day, and on the day after dosing or 2 days after dosing, depending on when the participant is admitted and discharged.
- ⁱ If a potential participant is rescreened, these assessments do not need to be performed again unless more than 12 months will have elapsed between each test and enrollment.
- ^j A window of ± 30 minutes from each time point is permitted for PK/PD timepoints except the PK sample collected at end of infusion (+ 15 minutes). Predose PK/PD windows are -1 hour (SC doses) and 3 hours (IV dose). For all assessments, their window and the visit window should not be calculated together to determine the permitted assessment time.
- ^k Asfotase alfa ADA and NAb will only be tested in participants who have previously received asfotase alfa. Participants do not need to be retested for ADAs and NAbs if they are re-screened.
- ¹ Each 12-lead ECG will be performed in triplicate (sequentially within a 15-minute period) and should not be assessed after any major meal (ie, major meals should be withheld until after ECG assessments). All ECGs should be performed before the vital signs assessment and PK/PD sampling (in that order if 1 or both of the latter are also scheduled during an ECG timepoint). Each ECG shown in this table has a window of \pm 30 minutes.
- ^m Injection/infusion site evaluations will be performed within 15 minutes (± 5 minutes) after injection/EoI and ± 15 minutes of the rest of the timepoints.

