7.2. Participant Discontinuation/Withdrawal from the Study

- All efforts should be made to ensure participants are willing to comply with study participation prior to conducting the screening procedures. The study staff should notify Alexion and their site monitor of all study withdrawals as soon as possible. The reason for participant discontinuation must be recorded in the source documents and eCRF.
- A participant may withdraw from the study at any time at his/her own request or may be withdrawn at any time at the discretion of the Investigator for safety, behavioral, compliance, or administrative reasons.
- At any visit, a positive drug test result for a non-prescribed substance will lead to participant discontinuation.
- A positive pregnancy test result at any time during the study will lead to participant discontinuation.
- Participants diagnosed with COVID-19 with clinical manifestations of the disease will be evaluated for potential treatment and/or study discontinuation according to the CRU's COVID-19 protocol.
- At the time of discontinuing from the study, if possible, an Early Discontinuation visit should be conducted, as shown in the SoA. See SoA (Section 1.3) for data to be collected at the time of discontinuation and follow-up and for any further evaluations that need to be completed.
- If the participant withdraws consent for disclosure of future information, Alexion may retain and continue to use any data collected before such a withdrawal of consent.
- If a participant withdraws from the study, he/she may request destruction of any samples taken and not tested, and the Investigator must document this in the site study records.
- Participants who withdraw/are withdrawn from the study following completion of EoT assessments but prior to completion of EoS assessments will be considered "completed" if all PK/PD sampling was performed within window and all doses were administered per the SoA. "Completed" participants do not need to be replaced.

Page 48 of 97	
Alexion Confidential	

- Participants who withdraw/are withdrawn from the study prior to completion of the end-of-treatment assessments should be replaced unless at least 3 participants in their cohort have already "completed" or are on track to "complete".

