8.2.6. Pregnancy

Pregnancy data from female participants and female spouses/partners of male participants will be collected from the first dose of ALXN1850 and at the time points specified in the SoA (Section 1.3). Any female participant who becomes pregnant during the study should be considered for discontinuation from the study intervention. If a pregnancy is reported, the Investigator must immediately inform Alexion within 24 hours of awareness of the pregnancy and follow the procedures outlined in Section 10.4.3.

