5.1. Disposition

Using the enrolled set, the screen failure of participants will be summarized with counts and percentages by overall. A summary table will include the following:

- Number of participants in the enrolled set (ie, all participants who signed the informed consent form [ICF])
- Number of participants who were screen failures
- Number of participants who received a dose
- Number of participants who failed screening due to COVID-19 related reasons
- Reason for screen failure that was not due to eligibility
- Reason for screen failure that was due to eligibility

Based on the Safety Set, the analysis sets will be summarized with counts and percentages by cohort and overall. A summary table will include the following:

- Number of participants included in PK Set
- Number of participants excluded from the PK Set
- Reason for exclusion from the PK Set
- Number of participants included in PD Set
- Number of participants excluded from the PD Set
- Reason for exclusion from the PD Set
- Number of participants included in Immunogenicity Set
- Number of participants excluded from the Immunogenicity Set
- Reason for exclusion from the Immunogenicity Set

Using the Safety Set and PK Set, the disposition of participants will be summarized with counts and percentages by cohort and overall. A summary table will include the following:

Statistical Analysis Plan, Version 1.0 Date Issued: 26/04/2022

- Number of participants who completed the study
- Number of participants who discontinued the study
- Reasons for discontinuation
- Number of participants who discontinued the treatment
- Reasons for treatment discontinuation
- Number of participants who were discontinued due to COVID-19

Screen failure data will be presented in a data listing for all screen failure participants. Participant disposition data and analysis sets will be presented in separate data listings for the Safety Set.

5.2. **Protocol Deviations**

The protocol deviations will be summarized by cohort and overall for the Safety Set. Protocol deviations will be classified as important and not important.

All protocol deviations will be presented in a data listing for the Safety Set.

5.3. **Inclusion and Exclusion Criteria**

Inclusion and exclusion criteria deviations will be presented in a data listing for the Safety Set.

6. Demographics and Baseline Characteristics

Demographics 6.1.

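### The protocol gives three different rules for a participant who becomes pregnant, and they disagree on whether dosing must stop and whether she stays in the study

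*Protocol*

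**What the plan says.** Four places in the current protocol (Amendment 5) state what happens to a participant who becomes pregnant.

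- Section 7.2, whose heading covers discontinuation and withdrawal from the study: "A positive pregnancy test result at any time during the study will lead to participant discontinuation".
- Section 8.2.6: "Any female participant who becomes pregnant during the study should be considered for discontinuation from the study intervention". It then sends the investigator to Section 10.4.3 for procedures.
- Section 10.4.3 repeats the Section 8.2.6 rule: she "should be considered for discontinuation from the study intervention".
- Section 10.4.3.2, a subsection of 10.4.3 and the one specific to female participants: she "will discontinue study intervention but will not be withdrawn from the study".

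None of this is amendment-log text, and nothing says which section governs.

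**The concern.** A site needs two answers after a positive test: whether the next dose may be given, and whether the participant stays in the study. The four sections do not give the same answer to either. Depending on the section consulted, a site could treat stopping drug as optional, could stop drug and keep her in follow-up, or could discontinue her from the study. Section 8 allows no protocol waivers, so a site that follows one section as written may deviate from another.

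The consequence falls first on the participant, through further exposure to a first-in-human product or early loss of scheduled safety and antidrug antibody (ADA) visits. There is a smaller effect on the data: whether she counts as a completer for her cohort, and how she is classified in the disposition summary.

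**Working it through.** No formula applies. The check is a side-by-side reading of the four sections, followed by the visit schedule and the counting rules.

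**1. The rules compared**

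| Protocol section | Must study drug stop? | Does she stay in the study? |
|---|---|---|
| 7.2 | Yes | No, on the natural reading (step 2) |
| 8.2.6 | To be considered | Silent |
| 10.4.3 | To be considered | Silent |
| 10.4.3.2 | Yes | Yes |

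That makes three distinct rules in four places. The first column conflicts between the two middle rows and the other two. The second column conflicts between 7.2 and 10.4.3.2.

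**2. What discontinuation means in Section 7.2**

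The pregnancy bullet does not itself add that the discontinuation is from the study. Two things point that way. The section heading concerns leaving the study. The neighbouring drug-test bullet uses the same outcome wording, "At any visit, a positive drug test result for a non-prescribed substance will lead to participant discontinuation", and the Schedule of Activities footnotes (Section 1.3) spell out that outcome: "if positive, the participant will be discontinued from the study". If the bullet is nevertheless read as stopping drug only, the retention conflict disappears, but the conflict over whether stopping drug is mandatory remains.

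**3. When a site would face the decision (Section 1.3, Tables 1 and 2)**

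- Urine tests on the day before an SC dose: Days 14, 21 and 28 for the first participant in a cohort; Days 7, 14 and 21 for the others. That is 3 tests, each followed by a scheduled dose the next day.
- Urine tests after the last dose: Days 36, 51, 65 and 85, or Days 29, 43, 57 and 78. That is 4 tests at which no dose remains, so retention is the only open question.
- Follow-up at stake after the last dose: 85 − 29 = 56 days for first participants and 78 − 22 = 56 days for the others, which is 8 weeks in both cases, before visit windows.

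**4. Effect on cohort counts and disposition**

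Section 9.2 defines a completer as having all doses per schedule, all PK/PD samples within window and the end-of-treatment (EoT) assessments done. Section 7.2 sets the replacement rule: "Participants who withdraw/are withdrawn from the study prior to completion of the end-of-treatment assessments should be replaced unless at least 3 participants in their cohort". The rest of that sentence makes the exception depend on those three being actual or expected completers.

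- Positive test before the last dose, drug stopped: she cannot be a completer whether retained or withdrawn, because doses are missing. If a site relied on 8.2.6 and continued dosing, she still could be.
- Positive test after the last dose but before EoT (Day 65 or Day 57): if retained she can still be a completer; if withdrawn she is subject to replacement.
- Positive test after EoT: she can count as a completer either way.

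SAP Section 5.1 reports "Number of participants who discontinued the study" separately from those who discontinued treatment, so her classification depends on which protocol section the site followed.

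**The case against.** The best case for the current text is that the sections are closer than they look. Both 7.2 and 10.4.3.2 end dosing, and only the general sentence in 8.2.6 and 10.4.3 is softer; being considered for discontinuation is not permission to continue. Section 8.2.6 also directs the site to 10.4.3, where the most specific subsection gives a firm rule. This helps only in part. The cross-reference lands on 10.4.3, which repeats the soft sentence and so disagrees with its own subsection.

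The stronger part of the objection concerns lost follow-up. Several provisions apply even to a participant who leaves the study:

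- Section 7 asks dosed non-completers to make every effort to undergo the scheduled safety, PK and PD evaluations.
- Section 7.2 asks for an early discontinuation visit where possible, and the corresponding column of Table 1 includes ADA, chemistry, hematology and ECG.
- Section 8.9 asks for an immunogenicity sample at the final visit of withdrawn participants.
- Section 10.4.3.2 follows the pregnancy to outcome regardless of withdrawal.

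These stand, and they reduce the likely loss mainly to later scheduled ADA visits. They do not settle whether she is in the study or out of it, and they do not address dosing.

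It is also fair that the event is unlikely. The study is small, pregnancy is an exclusion criterion, a negative serum test is required at Screening and contraception is mandatory.

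**Conclusion.** The protocol contradicts itself. Whether study drug must stop is stated in two incompatible ways, and that holds on any reading of Section 7.2. Whether she stays in the study is also stated in two incompatible ways if 7.2 means discontinuation from the study, which its heading and the parallel drug-test rule support.

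The size is small in expected number and matters for the individual: a rare event among about 15 participants, affecting the next dose and up to 8 weeks of in-study follow-up, part of which other provisions protect. The effect on completer status is confined mainly to a positive test between the last dose and EoT. This is an internal contradiction that should be corrected; it does not threaten the study's analyses. It is not for this review to say which clinical rule is right.

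**What to change.** Reconcile Sections 7.2, 8.2.6, 10.4.3 and 10.4.3.2. The sponsor should choose one rule, state it in full in one section, and replace the other three statements with a cross-reference to it. The rule should answer two questions separately: what happens to study drug, and whether the participant remains in study follow-up. It should also cover a positive test after the last dose, when only the second question applies. Section 7.2 should say explicitly whether discontinuation there means study drug or the study.

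The SAP needs no new analysis. Once the rule is fixed, her place under study or treatment discontinuation in SAP Section 5.1 follows from it. The cost is wording in four protocol sections.
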